The proposed MPI consists of a medical consultation to optimise patients' treatment regimen, address concerns about their disease and treatment, explain advantages and disadvantages about the type of IVT medication and potential of increased treatment intervals between IVT, and address other patient and care-giver concerns.

Importantly, CAT scores will be available to the clinician to guide the consultation. Based on sub-optimal CAT scores, referral to one or a combination of services will be initiated by the study team according to a preset protocol (**Table 2**):

- (1) a referral to NE, which would include a session with a trained IVT nurse educator, who would use previously validated hard copy and digital education resources to educate the patients on their disease, symptoms, progression, and need for treatment. Factors which may cause anxiety for IVT patients such as side effects and adverse events will be addressed and the need for IVT adherence to maintain long-term vision will be reinforced. The patients would be reminded about the availability of the IVT hotline to address concerns and appointment issues.

- (2) a referral to OP who, after a needs assessment, would then carry out a comprehensive low vision assessment that includes refraction, CS, reading acuity, determination of reading goals and prescribing of suitable optical aids. OPs will assess and address any vision-related issues that may hinder reading specific tasks, navigation and other ADLs, which may be barriers to IVT adherence. They can further discuss the patient's expectations about their visual recovery and the need for IVT to maintain vision.
- (3) a referral to OT who, after a needs assessment, would provide advice about optimal lighting and, contrast perform activities of daily living retraining and functional/community mobility training, provide patient/family education and, if required, home modification to facilitate independence in ADLs, which may may allow better access to IVT appointments promoting adherence.
- (4) a referral to medical SW who, after a needs assessment, would provide the necessary emotional counselling, financial counselling and referral to community care services and other relevant support services addressing relevant barriers related to adherence to IVT.

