2. HYPOTHESIS AND OBJECTIVES

Specific aim 1: To assess the effectiveness of MPI, versus standard care, in improving adherence to IVT follow-up appointments at 6, 12 and 18 months (main timepoint for primary outcome) *in patients with nAMD and DME requiring long term management* (primary outcome).

Hypothesis 1: *Compared to those in standard care, patients in the MPI group will have higher adherence to long-term follow-up appointments and IVT therapy.*

Specific aim 2A: Assess the effectiveness of MPI, versus standard care, in improving domain-specific CAT scores at the various follow-up timepoints (secondary outcome).

Hypothesis 2A: *Compared to those in standard care, patients in the MPI group will have greater gains in domain-specific CAT scores at each follow-up time point.*

Specific aim 2B: Assess the effectiveness of MPI versus standard care in improving visual acuity (VA), contrast sensitivity (CS), disease free intervals between IVT (as measured on optical coherence tomography (OCT) (secondary outcomes).

Hypothesis 2B: *Compared to those in standard care, patients in the MPI group will have greater VA and CS gains and achieve longer disease-free intervals between IVT at each follow-up time point.*

Specific Aim 3: To assess implementation outcomes of the MPI such as acceptability, adoptability, appropriateness, feasibility, fidelity.

Hypothesis 3: *Using a mixed methodology, with quantitative and qualitative outcome measures as reported by patients, caregivers, clinicians, nurses and allied health professionals, MPI will be an appropriate, adoptable, acceptable, feasible intervention with good fidelity.*

Specific Aim 4: To assess the cost-effectiveness of the MPI for improving adherence to IVT, considering its potential impact on long term visual acuity (VA) loss and QoL adjusted years (QALYs)

Hypothesis 4: *The MPI is incrementally cost-effective relative to standard care, based on accepted willingness-to-pay thresholds⁴².*

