8.2. Statistical and Analytical Plans

Specific aim 1: Planned statistical analysis for the primary outcome measure will be the difference in percentage of adherence rate between the standard care and MPI arm assessed by the chi-square test or Fisher's exact test. Cox proportional hazards model will be used to assess the independent effect of MPI on adherence rates, after adjusting for age, baseline CAT scores, visual function, anatomical outcomes, type of IVT medication given, and disease-free intervals.

Specific aims 2A and 2B: CAT scores will be assessed with a two-sample t-test to compare the differences in mean CAT scores between the 2 arms. Linear mixed models will be used to assess the independent effect of MPI on follow-up CAT scores, after adjusting for fixed effects terms such as age, baseline CAT scores, visual function, anatomical outcomes, type of IVT medication given, and disease-free intervals, and a random slope term follow-up time (measured in months).

Specific aim 3 Interviews will be conducted in-person or online, audio-recorded, and transcribed verbatim by professional transcribers (i.e. transcriptions outsourced to third party). Designated researchers in the study team will check a random 10% sample of interview transcriptions for accuracy, prior to qualitative data analysis. If errors or inaccuracies are found in the random sample of transcripts, then 100% of the transcripts will need to be checked and edited for accuracy, prior to data analysis. We will analyse the qualitative data as per Gale et al's thematic analysis⁶². NVivo software will be used to manage qualitative data analysis. A standardised questionnaire to assess implementation outcomes will also be administered to all the stakeholders for a quantitative assessment.

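### The adjusted models for adherence and CAT scores list covariates that the MPI is meant to change, and only the CAT score is fixed at baseline

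*Protocol*

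**What the plan says.** Protocol section 8.2 first compares adherence percentages between arms, "assessed by the chi-square test or Fisher's exact test". It then adds an adjusted model: "Cox proportional hazards model will be used to assess the independent effect of MPI on adherence rates". The covariates of this model are listed in the same sentence, which has the effect estimated "after adjusting for age, baseline CAT scores, visual function, anatomical outcomes, type of IVT medication given, and disease-free intervals".

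For CAT scores it plans a two-sample t-test, followed by a linear mixed model for the independent effect of the MPI, "after adjusting for fixed effects terms such as age, baseline CAT scores, visual function, anatomical outcomes, type of IVT medication given, and disease-free intervals".

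Three other places bear on these covariates:

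- Section 1, on the content of the MPI: the compulsory medical consultation is there to optimise the regimen, and is to "explain advantages and disadvantages about the type of IVT medication and potential of increased treatment intervals between IVT".
- Section 2, Hypothesis 2B: "patients in the MPI group will have greater VA and CS gains and achieve longer disease-free intervals between IVT at each follow-up time point".
- Section 5, study schedule and outcome measures: visual function and disease-free interval are secondary outcomes, assessed at baseline and at 6, 12 and 18 months. The disease-free interval is the longest injection interval without recurrence on OCT.

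**The concern.** Of the covariates that can change during follow-up, only the CAT score is tied to baseline. The other four are visual function, anatomical outcomes, drug given and disease-free interval. Two of them are named secondary outcomes, one is worded as an outcome, and one is chosen in the course of treatment. If follow-up values are entered, the models hold constant the things through which the MPI is supposed to work.

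What is at stake is the meaning of the adjusted estimates. The Cox model is the only adjusted analysis of the primary outcome that the protocol names, and the mixed model is the only longitudinal analysis of CAT scores. Both would be reported beside the crude tests as the independent effect of the MPI. If they disagreed with the crude tests, a reader could draw the wrong conclusion about whether the intervention works.

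**Working it through.** **1. Where each covariate stands in relation to randomisation**

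| Covariate in section 8.2 | Timing stated there | What the rest of the protocol says |
|---|---|---|
| Age | none needed | not changed by the MPI |
| CAT score | baseline | measured before randomisation |
| Visual function | none | secondary outcome; improvement hypothesised (2B); measured at baseline and follow-up |
| Anatomical outcomes | none | worded as an outcome; OCT is reviewed through follow-up |
| Type of IVT medication given | none | discussed in the MPI consultation (section 1) |
| Disease-free interval | none | secondary outcome; lengthening hypothesised (2B); interval discussed in the MPI consultation |

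Disease-free interval and visual function may also follow from adherence. Adherence requires the injection within 1 month of the recommendation (section 5), and the disease-free interval is built from the injection intervals. Section 3 expects better adherence to give better disease control and less visual impairment. Section 8.2 (Aim 4) lets adherence drive long-term VA.

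Two problems follow if follow-up values are used. Holding a mediator constant removes the part of the MPI effect that passes through it. If the mediator and the outcome also share an unmeasured cause, conditioning on it links that cause to the arm and undoes the balance given by randomisation.

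**2. The plan's own figures, and whether they depend on this**

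Inputs from section 8.1: non-adherence 40% against 20%, power 80%, two-sided 5%, dropout 20%.

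- Primary: (0.4 × 0.6 + 0.2 × 0.8) × (1.960 + 0.842)² / 0.2² = 78.5, so 79 per arm. The plan rounds to 160 in total, and 160 / 0.8 = 200. This reproduces.
- Aim 2A: effect size 0.5 gives 63 per arm, and 126 / 0.8 = 157.5, so 158. This reproduces.

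Neither calculation uses the covariate list.

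**3. Illustration of size (assumed inputs)**

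The documents give no strengths for these paths, so the following shows a range only. Non-adherence was simulated for 200,000 patients per setting from a logistic model, tuned so that the true total effect is 40% against 20% (risk difference -0.20, odds ratio (0.20/0.80)/(0.40/0.60) = 0.375). One standardised covariate is shifted by the MPI by 0, 0.2 or 0.5 SD. It lowers the log odds of non-adherence by 0, 0.5 or 1.0 per SD. An unmeasured cause is either absent, or correlated 0.5 with the covariate and worth 0.8 on the log odds. The adjusted risk difference is standardised over the covariate.

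| Shift by MPI | Adjusted risk difference | Adjusted odds ratio |
|---|---|---|
| 0 | -0.196 to -0.202 | 0.29 to 0.38 |
| 0.2 SD | -0.154 to -0.198 | 0.38 to 0.39 |
| 0.5 SD | -0.093 to -0.201 | 0.37 to 0.56 |

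With a 0.5 SD shift and no effect of the covariate on adherence, the shared cause alone moves the risk difference to -0.164. The most extreme setting loses (0.200 - 0.093) / 0.200 = 54% of the effect. With no shift there is no bias on the risk-difference scale. The change in odds ratio in that row arises because the odds ratio changes with adjustment even without bias, so the risk difference is the fairer comparison.

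All runs assume that the MPI moves the covariate in the direction that lowers non-adherence. If a path ran the other way, holding it constant would make the adjusted effect larger than the total effect.

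**The case against.** The strongest reply is that section 8.2 does not say when these covariates are measured. Section 5 schedules VA, CS and disease-free interval at baseline as well as at follow-up, and the word baseline before the CAT scores could be read as carrying forward. In the mixed model the list is only illustrative. This stands in part. The reading is possible for visual function and perhaps for anatomy. It fits poorly for the drug given and for disease-free interval, and nothing in the protocol limits any of the four to values before randomisation.

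Several stronger readings are tempting, and the documents do not support them:

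- *That the primary comparison is biased.* It is an unadjusted chi-square or Fisher test, and CAT scores also have an unadjusted t-test.
- *That a disease-free interval cannot exist at baseline in a treatment-naïve patient.* Section 4.3 defines treatment-naïve as no IVT in the last 6 months. Such a patient may have had earlier injections, and section 7.1 allows records up to 10 years back. Previously treated patients are also eligible.
- *That Aim 2B outcomes are regressed on themselves.* The heading covers 2A and 2B, but the mixed model is written only for follow-up CAT scores.
- *That a definite share of the effect is lost.* Any percentage rests on assumed inputs, and the illustration is a logistic model, not the planned Cox model.

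**Conclusion.** The point holds for the two adjusted models. Followed as written, with follow-up values of visual function, anatomy, drug given or disease-free interval, neither model estimates the effect of being randomised to the MPI, and the label of independent effect would be wrong. The direction and size of the bias cannot be derived from the documents. The illustrated range of -0.09 to -0.20 at a 0.5 SD shift includes no bias at all, and it depends on the assumed directions and strengths. The conclusion rests on the four covariates being open to follow-up values, which the text permits and, for drug given and disease-free interval, suggests. The crude tests and the sample size stand.

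**What to change.** In section 8.2, state that every covariate in the Cox and linear mixed models is a value fixed before randomisation. A suitable list is age, diagnosis (the stratification factor), baseline CAT score, baseline VA and CS, baseline OCT anatomy, and prior treatment and adherence status. Remove drug given and disease-free interval during follow-up, and any follow-up visual function or anatomy, from both models. Values of these from before randomisation may be used where they exist. Because section 5 lets Cohort 2 patients be randomised at a later visit, define baseline for them in relation to randomisation.

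If the route by which the MPI works is of interest, analyse follow-up values in a separate mediation analysis, labelled exploratory.

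The cost is a change of wording. The protocol already schedules the baseline measures and the record review, so no new data and no change in sample size are needed. The change is most credible if made before outcome data are seen.

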- Following baseline assessment, **participants with suboptimal CAT scores (Cohort 1-<50 in any domain)** will be included in the RCT and randomly allocated in a 1:1 ratio to either the intervention group (personalised multi-disciplinary protocolised intervention, MPI) or the control group (standard care). Randomisation will be conducted using a computer-generated random sequence created by an independent biostatistician not involved in recruitment or outcome assessment. To ensure balance across disease types, randomisation will be stratified by diagnosis (neovascular age-related macular degeneration [nAMD] vs. diabetic macular edema [DME]). Allocation concealment will be maintained using sequentially numbered, opaque, sealed envelopes prepared by an independent study coordinator. The envelopes will only be opened after baseline data collection to assign participants to their respective groups. Co-Is that are not treating clinicians and data analysts will remain blinded to group allocation, although masking of participants and principal investigator and Co-Is who are the treating clinicians will not be feasible due to the nature of the intervention.

- For the MPI arm, the CAT scores integrated into the electronic medical records will be used to formulate **an automated protocolized standardized MPI for all patients based on the domain specific scores that are sub-optimal** (See **Table 2**). All MPI patients will receive *a medical consultation (compulsory) and an addition of Intervention 1-4 (electives, 1) NE, 2) OP, 3) OT, 4) SW*. In the MPI arm, these referrals would be automatically triggered by the study team based on baseline CAT scores and the treating clinician will be informed. The MPI visits will take place on the same day as standard clinical visits where possible, however additional MPI study visits may be needed if there are scheduling challenges. Referral adherence to the MPI appointments and intervention will be assessed.

Sub-optimal scores are defined as any domain where the scores are below 50 at baseline or have reduced by 25% from the baseline visit. Table 2 summarizes the MPI interventions that are relevant to each CAT domain. A tailored MPI will be formulated and recommended to the patient at baseline, or at a follow-up time-points where domain scores decrease, and the MPI should be completed within 4 months.

Table 2: Standardised personalised MPI based on sub-optimal CAT domain-specific scores

| Ret CAT | | MacCAT | |

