8. SAMPLE SIZE AND STATISTICAL METHODS

8.1. Determination of Sample Size

Specific Aim 1 and 2: The primary outcome comparison of adherence rates to IVT treatment between the MPI arm versus standard care at various follow-up time points with 18 months as the main time point. It is estimated that the baseline non-adherence rate with standard care arm is 40% (SD=2). Considering a reduction of the non-adherence rate to 20% as a clinically significant difference, and assuming a power of 80% and a two-sided level of significance at 5%, the minimum sample size

required is 79 patients per arm (rounded up to 160 patients in total). Assuming a maximum 20% dropout in the study we estimate a sample size of 200 patients (Specific aim 1).

For secondary outcomes such as the improvement of QoL as assessed by the various CAT domain scores, we assume a modest effect size difference of 0.5 between the two arms. Using a power of 80%, a two-sided level of significance at 5%, and the maximum 20% dropout rate, we estimate the required sample size is 158 (79 per arm) (Specific aim 2A). Hence, this is included in the larger sample size calculated above.

Specific aim 3: There is no *a priori* sample size required for qualitative interviews. We will continue our semi-structured interviews until thematic saturation is reached (i.e. no new themes emerge). Based on previous studies by our group^{31,67}, we anticipate the need to interview between 5-10 participants for each stakeholder group to obtain data saturation, broadly: (a) clinicians using CATs and MPI, (b) NE, OP, OT and SW involved in administering MPI (c) patients involved in this study, and (d) caregivers of patients. For the purposes of estimating a budget for this grant proposal, we state an indicative sample size of 40 interview participants i.e. 10 in total for stakeholder group a and b, and 30 for stakeholder group c and d (patients and caregivers).

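### The supportive Cox model for adherence pools two diseases but adjusts for baseline CAT scores that differ by disease, omits diagnosis, and leaves the number of terms open with only about 48 events expected

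*Protocol*

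**What the plan says.** Protocol section 8.2, Specific aim 1, makes the chi-square or Fisher's exact test the planned analysis of the primary outcome. It then adds a Cox proportional hazards model to estimate the independent effect of MPI, "after adjusting for age, baseline CAT scores, visual function, anatomical outcomes, type of IVT medication given, and disease-free intervals". These are six covariates or covariate groups. Their coding and number of terms are not given, and diagnosis is not among them.

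Section 1 describes the CATs as specific to AMD and to DME. Table 2 in section 5 lists the domains:
- **Ret CAT (8):** visual symptoms, activity limitation, emotional, health concerns, convenience, lighting, social, economic.
- **MacCAT (5):** activity limitation, lighting, emotional, concerns, AMD management.

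Section 5 has patients "randomly allocated in a 1:1 ratio", stratified by diagnosis (nAMD or DME).

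Section 8.1 sets the size of the trial: "It is estimated that the baseline non-adherence rate with standard care arm is 40% (SD=2"), then "Considering a reduction of the non-adherence rate to 20% as a clinically significant difference", "assuming a power of 80% and a two-sided level of significance at 5"%. The result is "79 patients per arm (rounded up to 160 patients in total"), and then "Assuming a maximum 20% dropout in the study we estimate a sample size of 200 patients".

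**The concern.** A covariate in a pooled model has to mean the same thing for every patient in it. Baseline CAT scores do not meet that condition here. A DME patient has eight scores and an nAMD patient has five. Only three domain names are shared, and those come from separate item banks. The protocol works with domain scores throughout and defines neither a composite nor a common scale for the two instruments.

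The model also leaves out diagnosis. Diagnosis was used to stratify randomisation, and it determines which instrument a patient receives.

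Finally, the number of terms is open while the number of events is small. This is the only model said to give the independent effect of MPI on the primary outcome. If the CAT covariate is settled only once data are in hand, the choice can move the estimate, and the fuller choices push it away from the null.

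**Working it through.** **1. Reproduce the planned size (section 8.1).** Inputs: non-adherence 0.40 and 0.20, power 80%, two-sided 5%. With the unpooled normal approximation:

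n per arm = (1.96 + 0.842)² × (0.4×0.6 + 0.2×0.8) / 0.2² = 78.5, so 79.

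This matches the protocol. Two arms of 79 make 158, rounded to 160, and 160 / 0.8 = 200.

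**2. Expected events.** Take the event to be a patient becoming non-adherent by 18 months. The protocol does not define the Cox event, so this is an assumption.

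- 80 per arm: 80×0.40 + 80×0.20 = 32 + 16 = 48.
- 79 per arm: 31.6 + 15.8 = 47.4.
- 100 per arm, all observed: 40 + 20 = 60, an upper figure at these rates.

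**3. Number of terms.** The protocol gives no count, so two readings bracket it.

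- Lean: arm, age, one CAT summary, VA, CS, one anatomical term, one medication term and disease-free interval make 8. With a single visual-function term it is 7.
- All domain scores: arm 1, age 1, CAT 8 + 5 = 13, VA and CS 2, anatomy 1, medication 1, disease-free interval 1, making 20.

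| Terms | Events per term, 48 events | Events per term, 60 events |
|---|---|---|
| 7 | 6.9 | 8.6 |
| 8 | 6.0 | 7.5 |
| 20 | 2.4 | 3.0 |

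**4. Complete covariates.** With 13 separate CAT columns, a DME patient has 8 filled and an nAMD patient 5. Nobody has 13, so a complete-case fit has no patients.

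**5. What the term count does to the treatment effect.** Three simulations used 160 patients, 80 per arm, with exponential times censored at 18 months. The true hazard ratio is ln 0.8 / ln 0.6 = 0.437, a log hazard ratio of −0.83. Simulation A used 1,000 runs per setting, CAT columns correlated at 0.5 and two weakly prognostic covariates. Simulations B and C used 3,000 null and 2,000 alternative runs, with covariates correlated at 0.4 and unrelated to outcome.

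| Terms | Simulation | Exaggeration of log HR | 95% interval coverage | Two-sided type I error |
|---|---|---|---|---|
| 5 | B | – | – | 5.1% |
| 5 | C | 4% | – | 5.3% |
| 7 | A | 3% | 94.7% | 6.1% |
| 20 | A | 10% | 93.6% | 8.6% |
| 20 | B | 13% | – | 7.4% |
| 20 | C | 13% | 92.8% | 6.9% |

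A dash means not reported. Simulation error on type I error is about 0.7 to 0.9 points in A and 0.4 to 0.5 in B. All fits in A converged. In A at 20 terms the mean estimate was −0.912, a hazard ratio of 0.40 against a true 0.44, and the mean standard error was 0.341 against an actual standard deviation of 0.368.

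Every simulated patient had all 20 columns. The results therefore show the cost of the term count, not the behaviour of a fit with one instrument's columns missing.

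**The case against.** The strongest reply is that the protocol names covariate groups, not parameters, and that choosing a CAT summary and coding the covariates is ordinary SAP work. One cut-off of 50 already applies to every domain of both instruments, so a summary is within reach. On the lean reading the distortion is small. Much of this stands. The protocol does not list 12 to 20 parameters; any count above 7 or 8 assumes that domain scores are entered. What remains is that the protocol commits a pooled model to scores that have no common form across its patients, and fixes a covariate list without the stratification factor. An SAP that followed the list literally would inherit both problems.

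Several stronger readings are tempting but unsupported:

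- **The model cannot be fitted.** That holds only if all 13 domains enter as separate columns and absent scores stay missing. A summary score can be fitted.
- **Separate models by disease would be far worse.** No split Cox model is planned. About 24 events per disease would also need an equal mix of nAMD and DME, which the protocol does not give.
- **Overfitting creates a claim for MPI when there is no effect.** Under the null the excess error falls equally on both sides: of 7.4%, about 3.7% would favour MPI, against a nominal 2.5%.
- **The primary result is at risk.** The chi-square or Fisher test uses none of these covariates.

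**Conclusion.** The point holds as a defect of the supportive adjusted model. Its CAT covariate is not common to the patients it pools, and diagnosis is missing from its list. At about 48 events it has 6 to 7 events per parameter on a lean reading, where simulated distortion is small (3% on the log hazard ratio with 7 terms). With every domain score it has 2.4, where distortion is modest: about 10 to 13% on the log hazard ratio and a type I error of about 7 to 9%.

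These figures assume that the planned rates are met, that the event is non-adherence by 18 months, that event times are continuous, and that the simulated correlations are reasonable. Events would be fewer if some of the 200 enrolled stay in Cohort 2 and are never randomised. The point does not depend on when the other covariates are measured; it stands even if all are taken at baseline. It merits a change to the text, but it does not threaten the primary analysis.

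**What to change.** In section 8.2, Specific aim 1:

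1. Replace baseline CAT scores in the Cox model with one pre-named baseline summary that every randomised patient has, for example the lowest domain score. Because this is a minimum over eight domains in one instrument and five in the other, it must be read together with diagnosis. A diagnosis term removes only an average shift between the two.
2. Add diagnosis as a covariate or as a stratum.
3. Limit the model to a short pre-named list of baseline terms suited to about 48 events: arm, diagnosis, age, CAT summary and baseline VA. Five terms give 48 / 5 = 9.6 events per term. The exact number is a rule of thumb; fixing a short list in advance is what matters.
4. Keep domain-specific baseline scores for the CAT outcome models under Specific aim 2A.

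The cost is protocol or SAP wording only, with no change to sample size, visits or data collection. The downside is fewer covariates in the supportive model.

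### Aim 2A compares each CAT domain over all randomised patients on an assumed 0.5 SD, although MPI referrals follow each patient's own sub-optimal domains, so the effect within a domain is diluted

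*Protocol*

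**What the plan says.** Entry to the randomised cohort (Protocol section 5) is for "participants with suboptimal CAT scores (Cohort 1-<50 in any domain"; one low domain suffices. Patients first placed in Cohort 2 can be randomised later, if a score drops below 50 or falls by 25% from baseline.

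The MPI arm receives "an automated protocolized standardized MPI for all patients based on the domain specific scores that are sub-optimal". Every MPI patient has the medical consultation. The four elective referrals (nurse education, optometrist, occupational therapist, social worker) are assigned by domain through Table 2.

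Hypothesis 2A (section 2) is that "patients in the MPI group will have greater gains in domain-specific CAT scores at each follow-up time point". Section 8.2 tests this by t-test: "CAT scores will be assessed with a two-sample t-test to compare the differences in mean CAT scores between the 2 arms". It adds a model: "Linear mixed models will be used to assess the independent effect of MPI on follow-up CAT scores, after adjusting for fixed effects terms", with baseline CAT score among those terms. Neither analysis distinguishes patients targeted in a domain from the rest.

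For the size of Aim 2A, section 8.1 says "we assume a modest effect size difference of 0.5 between the two arms". With 80% power, a 5% two-sided test and an allowance of 20% for loss, its result is: "we estimate the required sample size is 158 (79 per arm").

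**The concern.** The intervention is personalised by domain and the analysis is not. Take a DME patient whose only low RetCAT domain is Lighting. Table 2 sends that patient to the optometrist alone. Emotional, Convenience, Social and Economic map to the nurse educator, the social worker or both, and none of those referrals is triggered. The patient still counts in the arm comparison for each of those domains, starting from a score that was already acceptable.

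The arm difference in a domain is therefore a mixture of the effect in patients targeted there and a probably smaller effect in the others. If 0.5 SD is what the MPI achieves where it is aimed, the expected whole-arm difference is below 0.5, and a programme that works as designed could fail to show a difference for Hypothesis 2A. Section 1 lists quality of life among the outcomes on which the MPI is to be judged effective.

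**Working it through.** **1. The plan's own figure.** Per arm, n = 2(1.960 + 0.842)² / 0.5² = 62.8, so 63. With 20% dropout, 63 / 0.8 = 78.75, so 79 per arm and 158 in total. Section 8.1 reproduces exactly; the arithmetic is not at fault.

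**2. Numbers available.** The planned 200 less 20% leaves 160, or 80 per arm. I use 79 per arm, the evaluable minimum for Aim 1; using 80 changes power by less than one percentage point.

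**3. Dilution model.** Let f be the share of randomised patients sub-optimal in the tested domain, and s the effect in untargeted patients as a fraction of that in targeted ones. Then

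whole-arm effect d = 0.5 × [f + s(1 − f)].

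The protocol gives neither f nor s. I assume f = 0.3 to 0.7, with s = 0 (no spill-over) or s = 0.5. SD is 1 throughout.

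**4. Power of the t-test**, two-sided 5%, 79 per arm (noncentral t, noncentrality d√(79/2), 156 df):

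| f | d, s = 0 | Power | d, s = 0.5 | Power |
|---|---|---|---|---|
| 0.3 | 0.150 | 15.5% | 0.325 | 52.8% |
| 0.5 | 0.250 | 34.5% | 0.375 | 64.9% |
| 0.7 | 0.350 | 58.9% | 0.425 | 75.6% |
| 1.0 | 0.500 | 87.8% | 0.500 | 87.8% |

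Power of 80% needs d of about 0.449. That means f ≥ 0.449/0.5 = 0.90 without spill-over, or f ≥ 0.79 with s = 0.5 (from 0.5 + 0.5f = 0.897). At f = 0.5 and s = 0, 80% power would need 2(2.802)²/0.25² = 251.2, so 252 per arm.

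**5. Effect of baseline adjustment.** With correlation r between baseline and follow-up, the residual SD is √(1 − r²), so d is divided by that factor. The protocol gives no r.

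| f | s = 0, r = 0.5 | s = 0, r = 0.7 | s = 0.5, r = 0.5 | s = 0.5, r = 0.7 |
|---|---|---|---|---|
| 0.3 | 19% | 26% | 65% | 81% |
| 0.5 | 44% | 59% | 77% | 91% |
| 0.7 | 71% | 86% | 86% | 96% |

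**6. Would restricting each domain to its targeted patients solve it?** With f × 79 per arm and d = 0.5, unadjusted power is 39%, 59% and 74% for f = 0.3, 0.5 and 0.7. That beats the all-patient test when s = 0, but not when s = 0.5 (53%, 65%, 76%). Restriction domain by domain is not the remedy.

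**7. A score over each patient's own targeted domains.** Every randomised patient has at least one, so all 79 per arm remain. If the effect on that score is 0.5 SD, unadjusted power is 88%, whatever f and s are. That 0.5 is an assumption; the SD of such a score is not known.

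**The case against.** A reader might infer that the MPI acts only on domains below 50 and does nothing elsewhere. The documents do not support that. All MPI patients have the consultation, which addresses treatment, disease and caregiver concerns. A 25% fall also triggers the MPI. Table 2 shares referrals: in RetCAT the social worker serves Emotional, Health Concerns, Convenience, Social and Economic, and in MacCAT three domains have identical referrals. The s = 0 column is therefore a lower bound, and the Lighting-only patient is close to the extreme case.

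A reader might also infer that targeted and untargeted domains are averaged together. The outcomes are domain-specific and no cross-domain mean is stated. The dilution is across patients within a domain, and only within the instrument that contains that domain.

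The 0.5 is worded as a difference between arms and could already be a diluted figure. This stands as a possibility, but nothing says so. Without spill-over, a whole-arm 0.5 at f = 0.5 needs 0.5/0.5 = 1.0 SD in targeted patients; with s = 0.5 it needs 0.5/0.75 = 0.67 SD. Neither is obviously the modest effect that section 8.1 describes.

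The planned mixed model adjusts for baseline and recovers power. With r = 0.7 and half spill-over, power exceeds 80% over the whole assumed range of f. This stands and limits the point, although adjustment would help a targeted analysis equally.

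Finally, the all-randomised comparison is a valid estimate, it matches Hypothesis 2A, and a supportive analysis could sit in an unseen SAP. True, but section 8.1 itself fixes the 0.5 without saying to whom it applies.

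**Conclusion.** The point holds as a mismatch between a domain-targeted intervention, a whole-arm comparison in each domain, and an effect size with no stated allowance for untargeted patients. On the assumptions above, unadjusted power is 16–59% without spill-over and 53–76% with half spill-over, against 88% undiluted. Baseline adjustment raises these figures and, if the correlation is high and spill-over substantial, can restore 80%. The size of the loss cannot be settled from the protocol, because f, s and r are not given.

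It does not follow that the all-patient comparison is invalid or should be demoted, or that the sample size was miscalculated. This is a secondary aim, and the change is an inexpensive improvement worth making before the analysis is fixed.

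**What to change.** 1. In the secondary outcomes of section 5 and in section 8.2, keep the all-randomised domain comparisons and add a pre-specified targeted-domain analysis. For each patient, take the mean follow-up score over the domains that met the protocol's sub-optimal rule at randomisation: below 50, or the 25% fall that led to randomisation from Cohort 2. Including the fall matters, because a patient may be randomised on it with no domain below 50. Adjust for the same mean at randomisation and for diagnosis.
2. Alternatively, add an arm-by-targeted-domain term to the mixed model and report the arm effect in targeted domains.
3. State that the domains are fixed before allocation by the same rule in both arms, so that regression to the mean affects both alike. Do not select domains on falls after randomisation, which treatment can influence.
4. In section 8.1, say whether 0.5 is the whole-arm or the targeted-patient effect, and give the assumed f if it is the former.

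The cost is wording only, with no new data or visits. The drawback is that the targeted score mixes different domains across patients and across the two instruments, so the single-domain results must be shown beside it.
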